## 5 STUDY TREATMENTS

### 5.1 Treatment Groups

Following Screening/Enrollment and upon determination that a subject is heavily colonized with *S. aureus* as determined by a positive quantitative or semi-quantitative culture of an ETA (see Section 3.1), eligible subjects will be randomized in a 1:1 ratio to 1 of 2 treatment groups:

- ASN100 administered either sequentially or simultaneously as 2 separate IV infusions of ASN-1 and ASN-2, or
- Placebo administered either sequentially or simultaneously as 2 separate IV infusions.

Whether ASN-1, ASN-2, or placebo are administered sequentially or simultaneously will be determined by operational considerations of IV access at the time of dosing. If 2 IV lines are available for simultaneous administration this is preferable; however, if IV access or other considerations support sequential administration, this is allowed provided that both infusions are completed within 3 hours.

Following randomization on Day 1, subjects will receive either a single IV dose of 3600 mg of ASN100 (comprised of separate infusions each of 1800 mg ASN-1 and 1800 mg ASN-2) or matching placebos, per their assigned randomization scheme.

### 5.2 Stratification

To ensure balance among the treatment groups, randomization for this study will be stratified by receipt or non-receipt of concomitant anti-staphylococcal antibiotics at the time of randomization that are potentially active against *S. aureus* pneumonia, including, but not limited to, nafcillin, oxacillin, vancomycin, linezolid, telavancin, ceftaroline, ceftobiprole, and teicoplanin.

### 5.3 Rationale for Dosing

A series of PK and PD experiments was conducted using the rabbit *S. aureus* pneumonia model and measured PK in both healthy rabbits and rabbits with pneumonia caused by several *S. aureus* strains. The range of effective doses for preventing *S. aureus* pneumonia in animal models was 2.5 to 10 mg/kg of each component of ASN100. The 20 mg/kg dose (10 mg ASN-1 and 10 mg ASN-2) translated into a 1600 mg dose for an 80 kg subject.

ASN100 was well tolerated up to 8000 mg (i.e., 4000 mg ASN-1 and 4000 mg ASN-2) in a single-ascending dose study conducted in healthy human volunteers. There were no reported related SAEs and 2 related TEAEs of headache and fatigue were reported in this study. These data and data obtained from the nonclinical program determined that ASN100 3600 mg (i.e., 1800 mg ASN-1 and 1800 mg ASN-2) will be an appropriate dose to assess safety and efficacy in this first study in mechanically ventilated subjects who are heavily colonized with *S. aureus*.

This study did not identify a maximum tolerated dose. Based on these observations from the single ascending dose study, as well as data obtained from the nonclinical program conducted to date, it is reasonable to select a dose of ASN100 of 3600 mg (i.e., 1800 mg ASN-1 and 1800 mg ASN-2) as an appropriate dose to assess safety and efficacy in this first study in mechanically ventilated subjects who are heavily colonized with *S. aureus*.

## 5.4 Randomization and Blinding

Randomization will occur at the Randomization Visit following determination of the subject's eligibility. Subjects will be randomized via a centralized Interactive Response Technology (IRT) system in a 1:1 ratio to receive a single dose (2 infusions) of either ASN100 or matching placebo.

The study follows a double-blind, placebo-controlled design. All study personnel, including investigators, site personnel, site pharmacist, Sponsor and contract research organization (CRO) staff involved in the conduct of the study (e.g., clinical research associate [CRA]/monitor), and subjects will be blinded to treatment assignment. ASN100 and placebo will be identical in appearance to preserve blinding.

## 5.5 Breaking the Blind

Randomization data will be kept strictly confidential until the time of unblinding and will not be accessible by subjects, Investigators, or anyone performing assessments and having access to study data until unblinding occurs. Individual subject unblinding will only occur in the case of subject emergencies, with complete unblinding at the conclusion of the study.

Emergency breaking of the assigned treatment code should only be undertaken when it is essential that knowledge of the treatment assignment is necessary to treat the subject's emergency safely and effectively. Emergency treatment code breaks will be performed using the IRT. When the Investigator contacts the system to break a treatment code for a subject, he/she must provide the requested subject's identifying information and confirm the necessity to break the treatment code for the subject. The Investigator will then receive details of the investigational drug treatment for the specified subject and a fax or email confirming this information. The system will automatically inform the Sponsor and Medpace study personnel that the code has been broken.

## 5.6 Drug Supplies

### 5.6.1 Formulation and Packaging

ASN100 is a combination product with 2 separate human mAb components of the IgG1 isotype. The specific mAbs are formulated separately and called ASN-1 and ASN-2.

ASN-1 is a broadly cross-reactive anti-toxin mAb that targets Hla and 3 F-components (HlgB, LukF, and LukD) involved in forming 4 of the 5 bi-component leukocidins of *S. aureus*.

ASN-2 is directed against the fifth bi-component toxin of *S. aureus*, LukGH.

Each component is supplied as a sterile, colorless, clear liquid solution formulated ready for injection.

ASN-1 and ASN-2 will be supplied in separate 10 mL vials as a sterile solution for infusion with an extractable volume of 10 mL and a nominal mAb concentration of 20 mg/mL. Each vial will contain 200 mg of ASN-1 or 200 mg of ASN-2. Matched vials of ASN-1 placebo and ASN-2 placebo will also be provided.

Additional details regarding formulation and packaging will be provided in the Pharmacy Manual and the Investigator's Brochure.

### 5.6.2 Study Drug Preparation and Dispensing

Blinded study drug and reference preparations will be delivered to the study site. The site pharmacist will prepare the study drug for administration by extracting all volume from each set of 9 vials and inserting into an empty IV bag for each set, using aseptic technique according to the Pharmacy Manual. These will be delivered to the study site research staff in 2 blinded, ready-to-use infusion bags.

Additional details regarding study drug preparation and dispensing will be provided in the Pharmacy Manual.

### 5.6.3 Study Drug Administration

Subjects will receive ASN100 or matching placebo via 2 IV infusions over a duration of approximately 50 to 60 minutes per infusion.

Both ASN100 and placebo will be administered as 2 separate infusions (either sequentially or simultaneously). The last infusion will be completed within 5 hours from initiation of drug preparation in the pharmacy.

Infusions delivered simultaneously must be administered via distinct IV lines (either peripheral or central lines; in the instance that a multi-port central line is used, infusions will be delivered through separate ports) such that the infusions do not mix before entering the blood stream.

In the occasion that the 2 infusion bags cannot be hung simultaneously, the blinded IV bags will indicate which bag should be infused first and which bag should be infused second. If administered sequentially, no more than a 3-hour window should elapse from the time of initiation of the first infusion to the completion of the second infusion.

ASN100 will be administered as separate infusions of 1800 mg ASN-1 and 1800 mg ASN-2 (9 vials of each to be pooled aseptically according to the Pharmacy Manual into separate infusion bags) delivered either sequentially within a 3-hour window from the time of initiation of the first infusion to the completion of the second infusion, or simultaneously.

Placebo will be administered as separate infusions of 9 vials of ASN-1 placebo and 9 vials of ASN-2 placebo (vials to be pooled aseptically according to the Pharmacy Manual into separate infusion bags) delivered either sequentially within a 3-hour window from the time of initiation of the first infusion to the completion of the second infusion, or simultaneously.

The infusion catheter and tubing will be flushed with sterile saline for injection immediately before and following completion of the infusion.

Either infusion may be discontinued if deemed medically necessary at any time.

If the first infusion is stopped at any point due to the concern of an adverse event, the second infusion will not be administered.

Refer to the Pharmacy Manual for additional details regarding study drug administration.

#### 5.6.4 Treatment Compliance

Study drug will be administered at the clinical site by blinded study personnel. The date and time of administration, including start and completion times of each infusion, will be accurately logged in the source documentation. Due to the single dose design of this study, treatment compliance is anticipated to be high.

#### 5.6.5 Storage and Accountability

Study drug (ASN-1, ASN-2, and matching placebos) will be stored at 2°C to 8°C, will be protected from light, and will be kept in a secure area with access limited to authorized personnel. The primary packaging (vials) is to be kept within the secondary packaging (carton box).

Investigational site personnel (e.g., study pharmacist) will perform an ongoing inventory of study drug products. At the end of the study, a full reconciliation of drug inventory will be performed and the results of the inventory will be recorded in the drug accountability log. Any unused vials should be returned for destruction.

Additional details regarding study drug storage and accountability will be provided in the Pharmacy Manual.

### **5.7 Prior and Concomitant Medications and/or Procedures**

#### 5.7.1 Excluded Medications and/or Procedures

The use of any investigational product within 30 days prior to the Screening Visit (or 5 half-lives of the investigational product, whichever is longer) is prohibited. Any immunoglobulin preparation for any medical indication is prohibited through follow-up Day 90 of the study.

Prior use of ASN100, ASN-1, or ASN-2 is prohibited.

#### 5.7.2 Documentation of Prior and Concomitant Medication Use

All prior medications received by the subject within 14 days prior to study drug administration and any concomitant medications used throughout the duration of the study will be recorded in the source documents and on the appropriate eCRF. The medication name, route of administration, dose, frequency, indication, and duration of treatment (start and stop dates) will be recorded.

## 6 STUDY PROCEDURES

### 6.1 Informed Consent

Written informed consent will be obtained from all subjects prior to any study-specific procedures being performed. A separate consent will be obtained from those subjects who participate in the BAL fluid PK sub-study.

See Section 12.3 for additional details regarding informed consent.

### 6.2 Screening/Enrollment (Up to Day -14)

Screening/Enrollment may be performed up to 14 days prior to randomization. Subjects who meet all of the inclusion criteria and none of the exclusion criteria will be screened daily (while mechanically ventilated) for up to 8 days to identify those subjects who are heavily colonized with *S. aureus* (see Section 3.1).

Screening for heavy *S. aureus* colonization by ETA culture will continue on Day 11 and Day 14 provided the subject remains mechanically ventilated, for a total Screening Period of up to 14 days. Additional ETA screening may occur on Days 9, 10, 12, and 13 at the discretion of the Investigator and providing the subject remains mechanically ventilated.

Once an enrolled subject has an ETA culture reported positive for heavy *S. aureus* colonization and meets all of the inclusion and none of the exclusion criteria, they are eligible for randomization. If they are not randomized on this occasion according to the protocol, they are no longer eligible for continued ETA sampling and randomization, and will be discontinued from the study; however, if subjects are extubated and subsequently re-intubated/mechanically ventilated, they are eligible for re-screening as a new subject enrollment. Subjects who were previously randomized are not eligible to be re-consented and re-screened.

The following procedures will be performed during Screening/Enrollment:

- Obtain informed consent;
- Review inclusion and exclusion criteria;
- Record medical history;
- Record demographics;
- Record antibiotic and other medication history;
- Obtain height and body weight measurements;
- Perform complete physical examination;
- Obtain vital sign measurements, including oxygenation status;
- Perform pregnancy test for female subjects of childbearing potential only. Female subjects may be enrolled on the basis of a negative urine pregnancy test, pending the result of a negative serum pregnancy test prior to randomization;
- Assess ventilator device status;
- Perform chest X-ray or thoracic CT scan. A chest X-ray or thoracic CT scan obtained as part of standard of care within 24 hours prior to the initial Screening Visit is sufficient

provided there are no changes in the subject's clinical status (e.g., no change in ventilation status, secretions, or signs/symptoms that may be suggestive of pneumonia) within the 24 hours following imaging;

- Obtain ETA for culture;
- Assess for other *S. aureus*-associated infections; and
- Perform adverse event assessment (adverse events that occur between the time the subject signs the ICF and the Randomization Visit will only be recorded if related to a study-specific procedure).

### **6.3 Randomization Visit (Day 1 Pre-Dose)**

The Randomization Visit will occur pre-dose on Day 1. At the time of randomization, if a subject's screening ETA culture also shows heavy colonization of a Gram-negative organism (i.e., heavy co-colonization of both Gram-positive and Gram-negative organisms), the subject will not be randomized into the study; however, randomization should not be delayed while waiting for Gram-negative results if heavy colonization with *S. aureus* has been confirmed.

The following procedures will be performed at the Randomization Visit:

- Review inclusion, exclusion, and randomization criteria;
- Review and record medical history (if changes occurred since the Screening Visit);
- Review and record antibiotic and other medication history (if changes occurred since the Screening Visit);
- Perform limited physical examination (to include, at a minimum, a pulmonary examination [including auscultation]);
- Obtain vital sign measurements, including oxygenation status;
- Perform clinical laboratory assessments, including chemistry, hematology, coagulation, and urinalysis;
- Obtain a blood sample for procalcitonin testing;
- Assess ventilator device status;
- Perform chest X-ray or thoracic CT scan. A chest X-ray or thoracic CT scan obtained within 24 hours of the Randomization Visit is sufficient, provided there are no changes in the subject's clinical status (e.g., no change in ventilation status, secretions, or signs/symptoms that may be suggestive of pneumonia) since the time of imaging;

NOTE: Subjects who are heavily colonized and who would have otherwise qualified for randomization, but who are found to have already progressed to pneumonia, may be eligible to enroll in a site-specific pilot treatment sub-study. See [Appendix C](#) for criteria.

- Assess for clinical signs/symptoms of pneumonia (Section 7.4.2; Table 1);
- Assess for other *S. aureus*-associated infections;
- Obtain nasal swab specimens for culture (one from each nostril);

- Randomize to study treatment;
- Obtain a blood sample for ADA and assessment of pre-existing anti-*S. aureus* toxin antibodies;
- Perform 12-lead ECG;
- Record concomitant medications; and
- Perform adverse event assessment.

#### 6.4 Treatment Period (Day 1)

The following procedures will be performed on Day 1 following administration of study drug:

- Obtain vital sign measurements, including oxygenation status;
- Assess ventilator device status;
- Assess for clinical signs/symptoms of pneumonia (Section 7.4.2; Table 1);

NOTE: Subjects who had already progressed to pneumonia while being evaluated for randomization under the VAP Prevention study, and who met eligibility criteria for the pilot treatment sub-study, will have the same study assessments and protocol required procedures as outlined in this and subsequent sections of this protocol, however the nature of the assessments may vary slightly to accommodate the sub-study endpoint of resolution of pneumonia. See Appendix C for criteria.

- Assess for other *S. aureus*-associated infections;
- Administer study drug;
- Obtain a blood sample for PK measurement and assessment of anti-*S. aureus* toxin antibodies (to be collected immediately following the completion of the second infusion [+15 minutes] and at 6 hours [ $\pm 4$  hours] and 24 hours [ $\pm 6$  hours] post-dose);
- Track days on ventilator from randomization;
- Track days in ICU (or other observation area) from randomization;
- Record concomitant medications; and
- Perform adverse event assessment.

#### 6.5 Monitoring Period

##### 6.5.1 Day 2/Day 3 – Bronchoalveolar Lavage Fluid Pharmacokinetic Sub-Study

The following procedures will be performed 48 hours ( $\pm 36$  hours) post-dose (Day 2 or Day 3 depending on the time of study drug administration) for those subjects participating in the BAL fluid PK sub-study only or if BAL fluid is collected as part of a standard of care procedure for any subject at any other time post-randomization for any other reason:

- Obtain vital sign measurements, including oxygenation status;
- Assess ventilator device status;

- Perform chest X-ray or thoracic CT scan;
- Assess for clinical signs/symptoms of pneumonia (Section 7.4.2; Table 1);
- Assess for other *S. aureus*-associated infections;
- Obtain BAL fluid to determine ASN-1 and ASN-2 concentrations (48 hours [ $\pm 36$  hours] post-dose) for those subjects participating in the BAL fluid PK sub-study (if BAL fluid is collected as part of a standard of care procedure from any subject enrolled in the sub-study at any other time post-randomization for any other reason, if possible, a sample for PK analysis will also be obtained);
- Obtain a blood sample for PK measurement  $\pm 1$  hour relative to BAL fluid collection (including scheduled BAL fluid collection or if BAL fluid is collected as part of a standard of care procedure from any subject enrolled in the sub-study at any time post-randomization);
- Track days on ventilator from randomization;
- Track days in ICU (or other observation area) from randomization;
- Record concomitant medications; and
- Perform adverse event assessment.

#### 6.5.2 Day 2 to Day 21

The following procedures will be performed daily (unless otherwise indicated) from Day 2 to Day 21 while the subject is hospitalized. For subjects participating in the BAL fluid PK sub-study, procedures noted for the Day 2 visit only need to be performed 1 time:

- Perform limited physical examination (to include, at a minimum, a pulmonary examination [including auscultation]);
- Obtain vital sign measurements, including oxygenation status;
- Perform clinical laboratory assessments, including chemistry, hematology, coagulation, and urinalysis. Blood samples for chemistry, hematology, and coagulation will be obtained on Days 2 ( $+1$  day), 4 ( $\pm 1$  day), and 6 ( $\pm 1$  day) of the Monitoring Period, and twice weekly during Week 2 (Day 8 through Day 14) and/or Week 3 (Day 15 through Day 21) of the Monitoring Period while the subject remains hospitalized. Urine for urinalysis will be obtained on Day 6 ( $\pm 1$  day) of the Monitoring Period only;
- Obtain a blood sample for procalcitonin testing (on day of diagnosis of pneumonia only, if applicable);
- Assess ventilator device status (if applicable);
- Perform chest X-ray or thoracic CT scan (required during the Monitoring Period for those subjects presenting with signs and symptoms of a respiratory infection such as dyspnea, tachypnea, fever, or cough);
- Obtain adequate respiratory specimen for culture (if clinically indicated);
- Assess for clinical signs/symptoms of pneumonia (Section 7.4.2; Table 1);

- Assess for other *S. aureus*-associated infections;
- Obtain a blood sample for ADAs (to be obtained only upon discharge from the ICU, if discharge occurs prior to Day 22);
- Obtain a blood sample for PK measurement and assessment of anti-*S. aureus* toxin antibodies (Days 4 [ $\pm 1$  day], 7 [ $\pm 1$  day], and 14 [ $\pm 2$  days] only);
- Track days on ventilator from randomization;
- Track days in ICU (or other observation area) from randomization;
- Record concomitant medications; and
- Perform adverse event assessment.

### 6.5.3 Day 22

The following procedures will occur on Day 22 (+2 days):

- Perform limited physical examination (if subject is hospitalized) (to include, at a minimum, a pulmonary examination [including auscultation]);
- Obtain vital sign measurements, including oxygenation status;
- Perform pregnancy test for female subjects of childbearing potential only (additional pregnancy testing may occur throughout the duration of the study, per applicable country requirements);
- Perform clinical laboratory assessments including chemistry, hematology, coagulation, and urinalysis;
- Obtain a blood sample for procalcitonin testing;
- Assess ventilator device status (if applicable);
- Perform chest X-ray or thoracic CT scan (required during the Monitoring Period for those subjects presenting with signs and symptoms of a respiratory infection such as dyspnea, tachypnea, fever, or cough);
- Obtain adequate respiratory specimen for culture (if clinically indicated);
- Assess for clinical signs/symptoms of pneumonia (Section 7.4.2; Table 1);
- Assess for other *S. aureus*-associated infections;
- Obtain a blood sample for ADAs;
- Perform 12-lead ECG;
- Assess for survival and discharge disposition;
- Obtain a blood sample for PK measurement and assessment of anti-*S. aureus* toxin antibodies;
- Track days on ventilator from randomization;
- Track days in ICU (or other observation area) from randomization;

- Record concomitant medications; and
- Perform adverse event assessment.

## 6.6 Follow-Up Period

### 6.6.1 Day 28 (+2 Days) Follow-Up

The following procedures will occur during a follow-up telephone call or visit, if the subject remains hospitalized, on Day 28 (+2 days):

- Assess ventilator device status (if applicable); and
- Assess for survival and discharge disposition.

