### 6.6.2 Day 40 to Day 89 (Follow-Up Safety Visit)

For subjects who remain hospitalized between Day 40 and Day 90 at the institution where they receive study treatment, a follow-up safety visit will be performed on the day of discharge.

The following procedures will occur on the day of hospital discharge for subjects who are discharged between Day 40 and Day 90:

- Perform limited physical examination (to include, at a minimum, a pulmonary examination [including auscultation]);
- Obtain vital sign measurements, including oxygenation status;
- Assess ventilator device status (if applicable);
- Obtain a blood sample for ADAs;
- Perform 12-lead ECG;
- Assess for survival and discharge disposition;
- Obtain a blood sample for PK measurement and assessment of anti-*S. aureus* toxin antibodies;
- Track days on ventilator from randomization (if applicable);
- Track days in ICU (or other observation area) from randomization;
- Record concomitant medications; and
- Perform adverse event assessment.

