### 6.6.3 Safety Visit (Day 90 [ $\pm 7$ Days])

The following procedures will be performed at the Safety Visit on Day 90 ( $\pm 7$  days). If the subject is unable to return to the site, this visit may be conducted by telephone, with procedures performed as appropriate (i.e., concomitant medications and adverse events collected):

- Perform limited physical examination (to include, at a minimum, a pulmonary examination [including auscultation]);
- Obtain vital sign measurements, including oxygenation status;

- Assess ventilator device status (if applicable);
- Obtain a blood sample for ADAs;
- Perform 12-lead ECG;
- Assess for survival and discharge disposition;
- Obtain a blood sample for PK measurement and assessment of anti-*S. aureus* toxin antibodies;
- Track days on ventilator from randomization;
- Track days in ICU (or other observation area) from randomization;
- Record concomitant medications; and
- Perform adverse event assessment.

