## 9 SAFETY ASSESSMENTS

### 9.1 Adverse Events

An adverse event is defined as any untoward medical occurrence in a clinical investigation subject administered a pharmaceutical product, which does not necessarily have a causal relationship with this treatment. An adverse event can therefore be any unfavorable and/or unintended sign (including an abnormal laboratory finding), symptom, or disease temporally associated with the use of an investigational medicinal product, whether or not related to the investigational medicinal product. All adverse events, including observed or volunteered problems, complaints, or symptoms, are to be recorded on the appropriate eCRF.

Adverse events that occur between the time the subject signs the ICF and the Randomization Visit will only be recorded if related to a study-specific procedure. Beginning with randomization all adverse events, which include clinical laboratory test and physical examination variables, will be monitored and documented until study participation is complete. Subjects should be instructed to report any adverse event that they experience to the Investigator. Site personnel will ensure each adverse event is recorded on the appropriate adverse event eCRF.

Wherever possible, a specific disease or syndrome rather than individual associated signs and symptoms should be identified by the Investigator and recorded on the eCRF. However, if an observed or reported sign or symptom is not considered a component of a specific disease or syndrome by the Investigator, it should be recorded as a separate adverse event on the eCRF. Additionally, the condition that led to a medical or surgical procedure (e.g., surgery, endoscopy, tooth extraction, or transfusion) should be recorded as an adverse event, not the procedure.

Any medical condition already present at the time of randomization should not be reported as an adverse event unless the medical condition or signs or symptoms present at baseline change in severity or seriousness at any time during the study. In this case, it should be reported as an adverse event.

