### **9.3 Serious Adverse Event Reporting – Procedures for Investigators**

#### **Initial Reports**

Serious adverse events related to a study-specific procedure that occur between the Screening Visit and the Randomization Visit, and all SAEs occurring from the time of randomization until the Day 90 Safety Visit, must be reported to Medpace Clinical Safety within 24 hours of the knowledge of the occurrence (this refers to any adverse event that meets any of the aforementioned serious criteria). All SAEs that the Investigator considers related to study drug occurring after the Day 90 Safety Visit must be reported to the Sponsor.

To report the SAE, complete the SAE form electronically in the electronic data capture (EDC) system for the study. When the form is completed, Medpace Safety personnel will be notified electronically and will retrieve the form.

If the event meets serious criteria and it is not possible to access the EDC system, send an email to Medpace Safety at [[contact]](mailto:[contact]) or call the Medpace SAE hotline (phone number listed below), and fax the completed paper SAE form to Medpace (fax number listed below) within 24 hours of awareness. When the EDC system becomes available, the SAE information must be entered within 24 hours of the system becoming available.

Safety Contact Information: Medpace Clinical Safety

Medpace SAE hotline – USA:

[contact], Dial 3 or [contact], Dial 3

[contact] or [contact]

Email: [[contact]](mailto:[contact])

Medpace SAE hotline – Europe:

[contact]

[contact]

Email: [[contact]](mailto:[contact])

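### No adverse-event or concomitant-medication assessment is scheduled between Day 22 and Day 90 for subjects discharged before Day 40, and the existing Day 28 contact asks about neither

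*Protocol*

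**What the plan says.** **Collection promised.** Protocol Section 9.1 states: "Beginning with randomization all adverse events, which include clinical laboratory test and physical examination variables, will be monitored and documented until study participation is complete". Section 9.3 makes reportable "all SAEs occurring from the time of randomization until the Day 90 Safety Visit", within 24 hours of the site's knowledge. Section 5.7.2 has concomitant medications recorded for the whole study, and Section 5.7.1 bars immunoglobulin preparations through Day 90.

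**Collection scheduled.**
- Section 6.5.2 opens "The following procedures will be performed daily (unless otherwise indicated) from Day 2 to Day 21 while the subject is hospitalized", and its list includes "Perform adverse event assessment".
- Section 6.5.3 opens "The following procedures will occur on Day 22 (+2 days" and again lists AEs and concomitant medications.
- Section 6.6.1 opens "The following procedures will occur during a follow-up telephone call or visit, if the subject remains hospitalized, on Day 28 (+2 days" and lists only ventilator status, and survival with discharge disposition.
- Section 6.6.2 does list AEs and concomitant medications, but its visit takes place "on the day of hospital discharge for subjects who are discharged between Day 40 and Day 90".
- Section 6.6.3 (Day 90, plus or minus 7 days) lists both. If the subject cannot return, "this visit may be conducted by telephone, with procedures performed as appropriate", which the protocol explains as collecting concomitant medications and AEs.
- Section 6.7 gives an Early Termination Visit only to subjects withdrawn before Day 22.

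The AE and concomitant-medication rows are blank at Day 28 in protocol Appendix A, in Appendix C Section 10.1 (the treatment sub-study) and in SAP Table 1.

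**Later use of the data.** SAP Section 7.13.1 defines treatment-emergent events from the start of dosing and sets no upper limit. SAP Section 7.11.2 estimates *S. aureus* pneumonia by Day 90. SAP Section 7.12 forms subgroups by cardiac events and by multi-organ failure up to Day 90 or early termination.

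**The concern.** Safety and tolerability are part of the primary objective, and Sections 1.2 and 5.3 call this the first study in this population. Section 9.1 promises monitoring to the end of participation, but for a subject who leaves hospital before Day 40 no scheduled contact asks about AEs between Day 22 and Day 90. The Day 28 contact falls inside that interval and passes over the question.

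Non-serious events after Day 22 may be forgotten or misdated by the Day 90 visit. The site may learn late of SAEs treated at another hospital, because the 24-hour clock starts only with knowledge. A subject lost to follow-up after Day 22 may contribute no later AE data beyond what was volunteered. Treatment-emergent event tables that nominally run to Day 90 could then be less complete after Day 22 than before it, and so could any Day 90 variable built on AE records.

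**Working it through.** The documents state no figure for the interval between AE assessments, so there is none to reproduce. The check is calendar arithmetic on the visit schedule.

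**Inputs.** Day 22 visit: Day 22 to 24 (Section 6.5.3). Day 28 contact: Day 28 to 30 (Section 6.6.1). Day 90 visit: Day 83 to 97 (Section 6.6.3). Discharge-day visit: discharges from Day 40 only (Section 6.6.2).

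**Step 1: current gap for a subject discharged before Day 40.** Gap = Day 90 visit day minus Day 22 visit day. Share = gap divided by the Day 90 visit day.

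| Case | Gap | Share of follow-up |
|---|---|---|
| Nominal | 90 − 22 = 68 days | 68/90 = 76% |
| Shortest | 83 − 24 = 59 days | 59/83 = 71% |
| Longest | 97 − 22 = 75 days | 75/97 = 77% |

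**Step 2: subjects still in hospital after Day 22.** The daily list ends at Day 21. The next scheduled AE assessment after the Day 22 visit is the discharge-day visit, nominally 40 − 22 = 18 days later at the earliest. For a subject still in hospital at Day 90 it is the Day 90 visit, 68 days later. A discharge between the Day 22 visit and Day 39 falls under Step 1.

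**Step 3: gap if AEs were also assessed at Day 28.** Longest remaining gap = Day 90 visit day minus Day 28 contact day.

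| Case | Gap | Share of follow-up |
|---|---|---|
| Nominal | 90 − 28 = 62 days | 62/90 = 69% |
| Shortest | 83 − 30 = 53 days | 53/83 = 64% |
| Longest | 97 − 28 = 69 days | 69/97 = 71% |

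**Step 4: what Day 28 accounts for.** 68 − 62 = 6 of the 68 nominal days. The other 62 arise because nothing is scheduled between Day 28 and Day 90 for subjects discharged before Day 40.

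**The case against.** The strongest defence is that this is a deliberate and consistent design. The procedure lists and all three tables agree, and Day 28 exists to assess mortality. For a single dose, AEs are assessed daily in hospital to Day 21, then at Day 22 and Day 90. This stands: the documents do not contradict one another on what happens at Day 28.

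Second, collection does not stop when the schedule is silent. Section 9.1 tells sites to instruct subjects to report any AE, SAEs are reportable to Day 90, and an inpatient has a contemporaneous hospital record. Concomitant medications, including barred immunoglobulin, are asked about at Day 90 even by telephone. This stands too, and confines the concern mainly to non-serious AEs and SAEs treated elsewhere. It does not remove it, because these routes rely on recently ventilated patients volunteering events and on the site learning of them.

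Third, both arms follow one schedule under double-blinding. Nothing in the documents suggests that the gap favours either arm, and the primary efficacy endpoint closes before Day 22.

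A reader might go further in three ways that the documents do not support:
- That the gap exists because of what Day 28 omits. Day 28 accounts for about 6 of 68 days.
- That the typical survivor is affected. Neither document gives a distribution of discharge times.
- That discharges on Days 25 to 39 need an added visit with anti-drug antibody, pharmacokinetic and ECG assessments. The Day 22 visit already schedules these, between 25 − 24 = 1 and 39 − 22 = 17 days earlier, and the addition would do nothing for earlier discharges.

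Nor can all late AE data be said to rest on recall, given the reporting duties above. The Day 90 pneumonia estimate is affected only in part, since Section 9.1 generally treats pneumonia meeting the study definition as an efficacy outcome and not an AE.

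**Conclusion.** The gap is real. Subjects discharged before Day 40 have no scheduled AE or concomitant-medication assessment for 68 days nominally (59 to 75 over the windows), 71% to 77% of follow-up. Subjects still in hospital after Day 22 have none until discharge at Day 40 or later, or Day 90. Within the gap, AE capture depends on spontaneous reporting, on SAE reporting once the site knows, and on recall at Day 90.

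The lengths follow from the visit windows alone. How many subjects are affected and how many events would be missed cannot be derived from the documents. The link to the SAP's cardiac and organ-failure subgroups assumes that those variables draw on AE records; the SAP names no source for them.

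This is a modest weakness in safety ascertainment. It does not threaten the primary efficacy analysis, and there is no evidence of bias between arms. It merits correction because safety is a primary objective and the Day 28 contact already takes place.

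**What to change.** Add AE/SAE assessment and concomitant-medication review to the Day 28 contact in protocol Section 6.6.1, Appendix A, Appendix C Section 10.1 and SAP Table 1. The cost is a few more questions on a contact that is already planned, plus the amendment wording. It needs no new visit, blood sample or ECG.

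Because this takes the longest scheduled gap only from 68 to 62 days nominally (53 to 69 over the windows), the plan should also do one of two things for the remainder:
- State that AE data between Day 28 and Day 90 rest on spontaneous reporting and Day 90 recall, and present late events with that caveat.
- Add one optional AE telephone call in the interval. As an illustration, a call at the midpoint, (28 + 90)/2 = Day 59, would leave 90 − 59 = 31 days as the longest nominal gap, at the cost of one more contact per subject.
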